H1: Repeated bouts of exercise will continue to stimulate an acute catabolic response with an increase in bone resorption, as demonstrated by significant increases in serum CTX from before to after exercise in the 1st, 8th, and 16th exercise sessions.

SA2: Determine whether repeated exercise-induced increases in PTH generate an anabolic skeletal response over time, similar to the anabolic response to pharmacologic PTH analogs (teriparatide, abaloparatide). This will be evaluated by measuring the change in a serum marker of bone formation (i.e., increase in serum procollagen type 1 N-terminal propeptide; **P1NP**) from the 1st to the 16th exercise session.

H2: Exercise-induced increases in PTH will generate a chronic anabolic response in bone, as demonstrated by an increase in pre-exercise serum P1NP from the 1st to the 16th exercise session.

If the results of the POC phase **support H1** (significant catabolic responses) and **refute H2** (non-significant anabolic response), we will proceed to the RCT to determine whether Ca supplementation before exercise can attenuate the catabolic skeletal response and enhance skeletal adaptations to training.

Research Methods

A. Outcome Measure(s): Change in CTX from before to after exercise, Change in pre-exercise P1NP from 1st to 16th exercise session.

B. Description of Population to be Enrolled:

Participants. We will enroll female and male Veterans aged 25 to 45 y or 55 to 75 y. Eligible volunteers will be normally active (e.g., recreational cycling or walking) but will not participate in regular moderate-to-vigorous exercise. Women will be premenopausal with regular menstrual cycles or postmenopausal, defined as

absence of menses for at least 12 mo or, in those who underwent a hysterectomy, a serum follicle stimulating hormone (**FSH**) >30 mIU/mL.

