To achieve the Aims, markers of bone resorption and formation will be measured before, during, and after the 1st, 8th, and 16th exercise sessions. The exercise stimulus will be the same for all sessions. For each of these sessions, participants will arrive at the CTRC between 0700h and 0800h following an overnight fast. They will be asked to keep a record of what they ate the evening prior to the blood collection visit and will be asked to eat the same meal prior to all blood collection visits. An intravenous catheter for blood sampling will be positioned in a forearm vein. Participants will remain rested in a semi-recumbent position for ~15 min; a blood sample will be obtained at the end of this interval. After voiding, body weight will be measured, and participants will move to the treadmill and remain standing for 5 min before exercise. A second pre-exercise blood sample will be obtained immediately before exercise. This sampling paradigm will enable us to address the contention that positional changes have not been adequately considered in evaluating the changes in plasma volume in response to cycling and running.²⁸ After exercise, participants will remain in a semi-recumbent position during a 4-h recovery interval. They will be allowed water *ad libitum* during exercise and recovery. Water consumption and urine volumes will be recorded for calculation of plasma volume changes. A standardized snack will be provided after the 120-min blood draw. Macronutrient composition will be 50% carbohydrate, 35% fat, and 15% protein, and total energy content will be ~500 kcal for men and ~350 kcal for women. Participants will return to the CTRC between 0800h and 0900h the next morning after an overnight fast for the 24-h post-exercise blood sample.

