Blood and urine collections will be the same for each of the three exercise sessions. Two pre-exercise blood samples will be obtained as described in the preceding paragraph. Blood samples (~5 mL each) will also be obtained after 15, 30, 45 and 60 min of exercise, during the 4-h recovery as indicated in Fig 20, and 24 h after exercise. Urine samples will be obtained shortly after the completion of the exercise session and after 4 h of recovery; other voids during the recovery period will be pooled with the final sample. Urine will then be collected through the 24-h post-exercise visit. Urine and blood samples will be processed by the CTRC Core Laboratory and stored at -80°C. Samples from all 3 exercise sessions for an individual will be analyzed in batch to minimize between-batch variance. The exceptions to this will be the parameters measured in real time (hematocrit (**Hct**), iCa, pH) during the study visits by the iSTAT analyzer (Abbot Point of Care, Princeton, NJ). Urine samples will be assayed for total Ca (**tCa**) at the University of Colorado Hospital (**UCH**) Clinical Laboratory by indirect ion-selective electrode (Beckman Coulter Inc, Brea, CA, USA). Urine Ca concentration will be multiplied by void volume to calculate Ca loss for each time interval. Serum (or plasma) assays will include: **1**) PTH by chemiluminescent immunoassay (Beckman Coulter Inc; CTRC Core Lab), **2**) CTX by chemiluminescence (Immunodiagnostic Systems, Boldon Business Park, UK; CTRC Core Lab), **3**) P1NP by chemiluminescence (Immunodiagnostic Systems; CTRC Core Lab), **4**) tCa by indirect ion-selective electrode (Beckman Coulter Inc; UCH Clinical Lab), **5**) phosphorus (**PO4**) by colorimetry (UCH Clinical Lab), and **6**) hemoglobin (**Hgb**) by automated cell counter (UCH Clinical Lab). PTH, CTX, iCa, tCa, and PO4 concentrations during and after exercise will be adjusted for shifts in plasma volume as previously described.⁴

Participation in the study is considered completed when one of the following criteria is met:

- Participant completes the final study procedure
- Participant elects to withdraw from the study

- Study clinician decides to withdraw the participant because of a health or safety concern

Description, Risks and Justification of Procedures and Data Collection Tools:

Potential Risks:

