The main outcome for **Aim 2** is the change in pre-exercise serum P1NP ( $\Delta\text{P1NP}_{\text{PRE}}$ ) from the 1st to the 16th exercise session. If the exercise-induced increase in PTH is anabolic, the pre-exercise P1NP values are expected to increase over the 16 exercise bouts, just as basal P1NP increases in response to PTH analog therapy (Fig 12-14). The observed change will be tested using a 2-sided paired t-test to test the statistical hypotheses  $H_0: \Delta\text{P1NP}_{\text{PRE}}=0$  vs  $H_1: \Delta\text{P1NP}_{\text{PRE}} \neq 0$ . This test will be conducted only if the test for Aim 1 is significant. The relative increase in P1NP after 4 wk of teriparatide or abaloparatide therapy ranged from 80% to 138% in several studies, and estimated effect sizes ranged from 1.3 to 2.6. We will take a conservative approach to finding an anabolic signal with exercise and use an effect size that is 53% smaller than the smallest effect size for change in P1NP in response to teriparatide or abaloparatide (0.69). Under these conditions, a sample size of 24 will enable us to detect a change in  $\Delta\text{P1NP}_{\text{PRE}}$  from the 1st to the 16th exercise session with 90% power. We will enroll 30 Veterans to allow for 20% attrition.

We considered correcting the significance level (alpha) for multiple tests because we are conducting two tests in the POC study (CTX, P1NP). However, because the second hypothesis test of P1NP will be conducted only if the first hypothesis test of  $\Delta\text{CTX}$  is significant and a hierarchy of tests has been defined *a priori*, we chose to not correct the significance level.

The distributions of the outcome measures will be evaluated. All analyses will be performed using SAS 9.4 software (SAS Institute Inc., Cary, NC). If there are severe departures from a normal distribution, transformations (e.g., natural logarithm) will be applied as appropriate to achieve an endpoint that seems normally distributed. To minimize missing data, all participants will be informed of the importance of complete follow-up and encouraged to complete the study per the protocol. We will make substantial efforts to prevent missed exercise tests and samples. Monthly reports will be generated that summarize recruitment, accrual, and completeness of follow-up to allow research assistants to proactively follow-up with participants in a timely

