manner. Prior to beginning analyses described below to address study hypotheses, we will examine the data carefully to assess whether patterns of missing seem ignorable (MAR=missing at random) or non-ignorable (MNAR= missing not at random). If the former, we will employ likelihood-based methods that utilize all available data, adjusting for covariates that are associated with missingness. If missingness seems non-ignorable we will consider, as data permit, pattern mixture models. Sensitivity analyses may be carried out using multiple imputation approaches.

The primary analyses for Aims 1 and 2 utilize only a portion of the data that will be collected. Secondary analyses will take advantage of the rich data set generated during the POC phase and can be used to help guide decision-making for the RCT. A linear mixed model based on maximum likelihood with all available data will be conducted to evaluate changes in CTX, P1NP, and other secondary outcomes (iCa, tCa, PTH, PO4, Hct, urinary Ca excretion) during exercise and recovery and how responses change from the 1st to the 8th to the 16th exercise session. Secondary analyses will also be conducted to investigate, for example, whether responses are influenced by age, sex, bone turnover marker level at baseline, or absolute exercise intensity. Interaction terms of treatment variable and variable of interest will be included to test for heterogeneity of treatment effect.

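### P1NP is left off the plasma-volume adjustment list although the SAP models it over exercise and recovery beside adjusted CTX; only secondary analyses are affected

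*Protocol*

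**What the plan says.** Protocol section C.3 describes the sampling and the assays. On timing, "markers of bone resorption and formation will be measured before, during, and after the 1st, 8th, and 16th exercise sessions", so the formation marker is not a resting measurement only. The assay list includes "P1NP by chemiluminescence (Immunodiagnostic Systems; CTRC Core Lab" as its third item, in the same panel as PTH, CTX, total calcium and phosphorus. The adjustment sentence then reads "PTH, CTX, iCa, tCa, and PO4 concentrations during and after exercise will be adjusted for shifts in plasma volume". It names five analytes, and P1NP is not among them.

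The SAP's Data Analysis Plan specifies, as a secondary analysis, a linear mixed model "to evaluate changes in CTX, P1NP, and other secondary outcomes" across exercise and recovery, and across the three sampled sessions. It adds that the secondary analyses may help guide decisions about the RCT.

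The Aim 2 outcome is different. In the SAP it "is the change in pre-exercise serum P1NP", and the protocol's outcome list agrees: "Change in pre-exercise P1NP from 1st to 16th exercise session".

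On the baseline, section C.3 provides for one sample after about 15 minutes semi-recumbent. Then, after 5 minutes standing, "A second pre-exercise blood sample will be obtained immediately before exercise". Neither document says which of the two is the pre-exercise value.

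**The concern.** A serum concentration changes when the amount of marker changes, and also when the volume of plasma around it changes. The protocol treats the second cause as material: it records water intake and urine output in order to calculate plasma-volume change, and it corrects five analytes for it. P1NP is the only blood concentration in the secondary mixed model that is left uncorrected. The other uncorrected outcomes there are haematocrit, which serves as an index of the shift, and urinary calcium excretion, which is not a blood concentration.

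Followed as written, the plan would show a resorption curve with the fluid shift removed beside a formation curve with it left in, both from the same tubes. A reader could take a small rise in P1NP during exercise as an acute formation response when it is only haemoconcentration. At stake is the interpretation of the within-session P1NP curves, and whatever weight they carry in RCT planning.

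**Working it through.** **1. The plan's own Aim 2 figure.** Inputs from the SAP: effect size 0.69, 24 evaluable participants, two-sided paired t-test, alpha 0.05.

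- Noncentrality = 0.69 × √24 = 3.38, with 23 degrees of freedom.
- Power from the noncentral t distribution = 89.9%. The stated 90% reproduces.
- Enrolment: 24 / (1 − 0.20) = 30. This reproduces as well.

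**2. Does the missing adjustment enter that figure?** The adjustment applies to samples taken during and after exercise. The Aim 2 difference is pre-exercise P1NP at session 16 minus pre-exercise P1NP at session 1. No during- or post-exercise P1NP value enters it. Adding P1NP to the list therefore leaves power at 89.9% and the sample size at 24 evaluable, 30 enrolled.

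**3. Does it enter the rule for proceeding to the RCT?** The protocol's rule is that H1 is supported and H2 is not. H1 rests on CTX, which is on the list. H2 rests on pre-exercise P1NP. Neither uses an exercise or recovery value of P1NP.

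**4. Where it does enter.** The blood concentrations in the SAP's secondary model, set against the protocol's list:

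| Analyte | Modelled over exercise and recovery | Plasma-volume adjusted |
|---|---|---|
| PTH | yes | yes |
| CTX | yes | yes |
| Ionized Ca | yes | yes |
| Total Ca | yes | yes |
| PO4 | yes | yes |
| P1NP | yes | not listed |

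**5. Size of the artefact.** Let f be the fractional loss of plasma volume, with the amount of circulating P1NP unchanged. The apparent relative rise is 1/(1 − f) − 1. The documents give no value for f, so the range is an assumption.

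- f = 5%: 1/0.95 − 1 = 5.3%
- f = 10%: 1/0.90 − 1 = 11.1%

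The same loss would raise CTX by the same percentage, but CTX is corrected. The spurious gap between the two curves is therefore the full 5.3% to 11.1%.

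**6. Comparison between sessions.** The model also asks how responses change across sessions 1, 8 and 16. If f is the same at each session, the artefact has the same relative size each time and makes no relative difference between sessions. If f were 5% at one session and 10% at another, the apparent responses would differ by 11.1 − 5.3 = 5.8 percentage points with no biological change. The documents do not say whether f is stable over the training period.

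**The case against.** The strongest reply is that the omission is harmless where it counts. The trial's anabolic signal is a chronic rise in resting P1NP, not a within-session change, and the authors may have left P1NP off the list for that reason. Much of this stands: neither primary test nor the RCT rule is touched, as steps 2 and 3 show. It does not dispose of the point, because the SAP names P1NP among the outcomes modelled over exercise and recovery and gives those analyses a possible role in RCT planning.

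A second reply is that the size is assumed. That is correct. The documents contain no plasma-volume loss, and if volume rose above baseline in recovery the artefact would change sign. The percentages illustrate the mechanism and do not predict what will be seen. The adjustment method is also given by reference to a cited study, which might explain the omission or fix the reference sample; that cannot be checked here.

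A reader might infer two stronger things:

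- **That haemoconcentration biases the Aim 2 result.** It does not arise, because only pre-exercise values enter.
- **That the plan discards one of the two pre-exercise samples, and that averaging them would sharpen Aim 2.** The documents do not say that a sample is discarded; they are silent on how the two are used. Nor are the samples replicates. They differ in posture by design, to study positional plasma-volume change, and the standing sample falls outside the adjustment. A postural offset cancels between sessions 1 and 16 only if it is equal at both, which is an assumption. No within-session variance for P1NP is given from which a gain could be computed.

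**Conclusion.** The point holds in a limited form. The adjustment list omits P1NP without a stated reason, while the SAP models P1NP over the very samples to which the list applies. Any fall in plasma volume would then appear as a P1NP rise that CTX does not share: about 5% to 11% for an assumed loss of 5% to 10%, taking the circulating amount of P1NP as constant. The consequence is confined to the secondary within-session P1NP analysis and its informal use in planning the RCT. Aim 1, Aim 2, the Aim 2 power and the formal RCT rule stand as written.

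The undefined pre-exercise value is a smaller matter of missing detail. It deserves a sentence because the term appears in the Aim 2 endpoint and the baseline for the CTX change is equally unspecified, but nothing in the documents shows that either endpoint will be computed wrongly.

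**What to change.** In Protocol section C.3, add P1NP to the analytes adjusted for plasma-volume shift during and after exercise, and repeat the full list in the SAP beside the secondary mixed model. If the omission is deliberate, give the reason and state in the SAP that the within-session P1NP curves are unadjusted.

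As a clarification, state in the SAP which of the two pre-exercise samples is the baseline for P1NP and for CTX, which sample is the plasma-volume reference, and that the same choice applies at sessions 1, 8 and 16. In making that choice, note that recovery samples are taken semi-recumbent, so a standing baseline would mix a change of posture into the CTX response.

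The cost is a few sentences and a few lines of code. Haematocrit and haemoglobin are already collected, and the same plasma-volume correction is already planned for CTX. The adjustment needs no new samples or assays and does not change the sample size. The baseline choice should be recorded before the outcome data are examined.

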**Principal Investigator: [name]**

**Version Date: 03/03/2025    NCT ID: NCT05029128**

## **Data Analysis Plan**

The primary outcome for **Aim 1** is the change in CTX ( $\Delta\text{CTX}$ ) from before exercise to the peak value observed during 4 h of recovery, measured during the 1st, 8th, and 16th exercise sessions. The primary hypothesis is that there will be a significant  $\Delta\text{CTX}$  for all three exercise sessions. The changes will be tested based on a repeated measures model to test the statistical hypotheses  $H_0: \Delta\text{CTX}_j=0$  vs  $H_1: \Delta\text{CTX}_j \neq 0$ , where  $j$  denotes the exercise session. A single test will be conducted based on  $\Delta\text{CTX}_j$ , and differences and dependency across measures will be accounted for using an unstructured covariance matrix. This will enable testing of a single hypothesis to make decisions regarding  $\Delta\text{CTX}$ .

**Power (Aim 1):** Attrition in our previous studies has been minimal (<10%), we have accounted for 20% attrition. The plan to enroll 30 participants (based on Aim 2) will ensure >99% power to address the hypothesis for Aim 1 in the full cohort and will also support secondary analyses of the sex specificity of the response. Based on our previous studies of older adults,  $\Delta\text{CTX}$  is expected to be 0.15 ng/mL and the standard deviation (**SD**) is expected to be 0.12 ng/mL, which corresponds to a standardized effect size of 1.25 (Cohen's  $d=1.25$ ). With statistical significance defined as  $p \leq 0.05$ , a sample size of 24 for a paired t-test will provide >99% power. Alternatively, with 90% power, we will be able to detect an effect size of 0.69. In addition, because the test will utilize a repeated measured model, it will have higher power than the paired t-test. The goal is to enroll 15 women and 15 men and expanding the age range to include Veterans aged 25 to 45 y will enhance the recruitment of women Veterans. We have not observed sex differences in the CTX response to exercise in previous studies, so an imbalance in sex should not influence the results. Our expectation is that the increase in serum CTX that we and others have observed in response to 1 or 2 exercise session in participants across a wide range of fitness (young, older, normally active, highly trained) will occur during the 1st, 8th, and 16th exercise sessions. A single test across all three time points will provide more power than multiple paired t-tests to evaluate the change in CTX at these time points. A significant test will be interpreted as evidence that exercise has an acute *catabolic* effect on bone that persists with exercise training.

The main outcome for **Aim 2** is the change in pre-exercise serum P1NP ( $\Delta\text{P1NP}_{\text{PRE}}$ ) from the 1st to the 16th exercise session. If the exercise-induced increase in PTH is anabolic, the pre-exercise P1NP values are expected to increase over the 16 exercise bouts, just as basal P1NP increases in response to PTH analog therapy (Fig 12-14). The observed change will be tested using a 2-sided paired t-test to test the statistical hypotheses  $H_0: \Delta\text{P1NP}_{\text{PRE}}=0$  vs  $H_1: \Delta\text{P1NP}_{\text{PRE}} \neq 0$ . This test will be conducted only if the test for Aim 1 is significant. The relative increase in P1NP after 4 wk of teriparatide or abaloparatide therapy ranged from 80% to 138% in several studies, and estimated effect sizes ranged from 1.3 to 2.6. We will take a conservative approach to finding an anabolic signal with exercise and use an effect size that is 53% smaller than the smallest effect size for change in P1NP in response to teriparatide or abaloparatide (0.69). Under these conditions, a sample size of 24 will enable us to detect a change in  $\Delta\text{P1NP}_{\text{PRE}}$  from the 1st to the 16th exercise session with 90% power. We will enroll 30 Veterans to allow for 20% attrition.

We considered correcting the significance level (alpha) for multiple tests because we are conducting two tests in the POC study (CTX, P1NP). However, because the second hypothesis test of P1NP will be conducted only if the first hypothesis test of  $\Delta\text{CTX}$  is significant and a hierarchy of tests has been defined *a priori*, we chose to not correct the significance level.

The distributions of the outcome measures will be evaluated. All analyses will be performed using SAS 9.4 software (SAS Institute Inc., Cary, NC). If there are severe departures from a normal distribution, transformations (e.g., natural logarithm) will be applied as appropriate to achieve an endpoint that seems normally distributed. To minimize missing data, all participants will be informed of the importance of complete follow-up and encouraged to complete the study per the protocol. We will make substantial efforts to prevent missed exercise tests and samples. Monthly reports will be generated that summarize recruitment, accrual, and completeness of follow-up to allow research assistants to proactively follow-up with participants in a timely

manner. Prior to beginning analyses described below to address study hypotheses, we will examine the data carefully to assess whether patterns of missing seem ignorable (MAR=missing at random) or non-ignorable (MNAR= missing not at random). If the former, we will employ likelihood-based methods that utilize all available data, adjusting for covariates that are associated with missingness. If missingness seems non-ignorable we will consider, as data permit, pattern mixture models. Sensitivity analyses may be carried out using multiple imputation approaches.

The primary analyses for Aims 1 and 2 utilize only a portion of the data that will be collected. Secondary analyses will take advantage of the rich data set generated during the POC phase and can be used to help guide decision-making for the RCT. A linear mixed model based on maximum likelihood with all available data will be conducted to evaluate changes in CTX, P1NP, and other secondary outcomes (iCa, tCa, PTH, PO4, Hct, urinary Ca excretion) during exercise and recovery and how responses change from the 1st to the 8th to the 16th exercise session. Secondary analyses will also be conducted to investigate, for example, whether responses are influenced by age, sex, bone turnover marker level at baseline, or absolute exercise intensity. Interaction terms of treatment variable and variable of interest will be included to test for heterogeneity of treatment effect.

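### Aim 1 tests a peak recovery CTX change against zero, but with repeated sampling the peak change averages above zero even without an exercise effect, so the 5% error rate is not held

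*SAP*

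**What the plan says.** The SAP (Data Analysis Plan, Aim 1) takes ΔCTX "from before exercise to the peak value observed during 4 h of recovery" at sessions 1, 8 and 16. On the test it states: "The changes will be tested based on a repeated measures model to test the statistical hypotheses", with a null of zero change in each session, a two-sided alternative, one overall test and an unstructured covariance. The Power (Aim 1) paragraph says that ΔCTX "is expected to be 0.15 ng/mL", that its SD "is expected to be 0.12 ng/mL", and that "a sample size of 24 for a paired t-test will provide >99% power". A significant result is to be read as a catabolic effect that persists with training.

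The protocol's outcome entry (Research Methods, A) is shorter: "Change in CTX from before to after exercise". Section C.3 draws two pre-exercise samples per session, one semi-recumbent and one standing, followed by samples during exercise, during the 4-h recovery and at 24 h. The recovery times are in a figure not shown, but a 120-min draw is mentioned in the text. Section C.2 gives every participant the same exercise, and no resting session is described.

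The SAP runs the Aim 2 test only if Aim 1 is significant and relies on that order to leave alpha uncorrected. The protocol (Specific Aims) starts the RCT if H1 is supported and H2 refuted.

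**The concern.** The highest of several noisy measurements is on average above any one of them. If CTX stays flat through a session, each recovery sample has the same mean as the baseline, but the highest one does not. The mean of peak minus baseline is then positive, and a test against zero rejects more often than 5%. A resting control would carry the same bias and cancel it, but this design has none. Neither document offers a non-zero null, a fixed time, a mean, an AUC or any other correction in the primary test.

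Three uses of the result depend on this test. It opens Aim 2, and the argument for leaving alpha uncorrected holds only if the first test is itself a 5% test. It is one of the two conditions for the RCT. It is also to be read as persistence of the response, so the exposure is greatest if the true response has faded at sessions 8 and 16, because the peak definition keeps the expected change there above zero.

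**Working it through.** **1. The plan's own figures.** d = 0.15/0.12 = 1.25. A two-sided paired t-test with n = 24 (23 df, noncentral t) has power above 99.9% at d = 1.25 and 89.9% at d = 0.69. The detectable effect at 90% power is 0.691. Enrolment is 24/0.8 = 30. The stated figures reproduce.

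**2. Model under no exercise effect.** For one person in one session, change = shared person-by-session term + highest of k recovery noise terms − baseline noise. Each noise term is normal with SD σ. The SD of a single recovery-minus-baseline difference is held at the SAP's 0.12 ng/mL. Let f be the share of that variance that is sample noise:

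2σ² = f × 0.12², so σ = 0.12 × √(f/2).

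Two inputs are assumptions: k = 2 to 8, because the sampling figure is not shown, and f, because neither document gives assay or within-session variability.

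**3. Bias.** Mean spurious change = E(k) × σ, where E(k) is the expected maximum of k standard normal values: 0.564 for k = 2, 1.03 for k = 4, 1.42 for k = 8. For f = 10%, σ = 0.12 × √0.05 = 0.0268, so the bias is 0.564 × 0.0268 = 0.015 (k = 2) to 1.42 × 0.0268 = 0.038 (k = 8).

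**4. False rejection.** Simulated trials with n = 24, three independent sessions and two-sided 5%. The SAP's single test is read as a joint 3-df test with unstructured covariance (Hotelling T²). Rates carry up to about one percentage point of simulation error.

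| Noise share f | σ (ng/mL) | Bias, k = 2 to 8 (ng/mL) | Joint test, false rejection |
|---|---|---|---|
| 2% | 0.012 | 0.007–0.017 | 6–13% |
| 5% | 0.019 | 0.011–0.027 | 8–28% |
| 10% | 0.027 | 0.015–0.038 | 11–55% |
| 25% | 0.042 | 0.024–0.060 | 23–94% |
| 100% (upper bound) | 0.085 | 0.048–0.121 | 82–100% |

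From 2% to 25% noise, the bias is 0.007/0.15 ≈ 5% to 0.060/0.15 = 40% of the planned effect. A test on one session alone rejects less often: 7–18% at 5% noise (k = 2 to 8), and 15–33% at 10% noise (k = 3 to 8).

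**5. Baseline.** Averaging the two pre-exercise samples leaves the bias unchanged, since it comes from the recovery maximum. It also reduces the variance, so false rejection rises: in the all-noise case with k = 2, the joint test goes from 82% to 94%.

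**6. Replacing the peak.** With the mean of four recovery samples, null rejection is 4.9% (joint), 5.1% (three-session average) and 4.9% (one session). One fixed recovery time gives about 5% on all three.

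**The case against.** The strongest reply is that the size is unknown and may be small. At 1–2% noise and few samples, the error rate is close to nominal. This stands: the mechanism is certain for k ≥ 2, but the magnitude is conditional. A reader might infer from the last row of the table that the test rejects almost always. The documents do not support that, because it needs the whole 0.12 SD to be sample noise, with no difference between people in their response.

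The SAP also plans a secondary mixed model for CTX on all available data, and says that secondary analyses can help guide the RCT. That model can estimate time-specific changes without taking a maximum, which is a real mitigation, but it is not the gate.

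If the bias is similar at each session, it largely cancels in comparisons between sessions. That also stands, so the problem is confined to the test against zero. A fall in CTX unrelated to exercise could offset the bias (at k = 4 with independent noise, a fall of about 1σ restores roughly 5%), but without a control nobody could tell.

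A false Aim 1 result does not start the RCT alone, because H2 must also be refuted. This protects little: if P1NP does not change, a 5% test is non-significant about 95% of the time.

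Three further inferences go too far. The documents do not specify a single baseline sample; two are drawn and their use is unstated. The protocol's brief outcome wording does not contradict the SAP, which makes it specific. The snack ("A standardized snack will be provided after the 120-min blood draw") is standardized and collections are the same at all three sessions, and the documents give neither direction nor size for any effect on CTX.

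**Conclusion.** The point holds. As written, the Aim 1 null is not the value that the mean peak change takes when exercise has no effect, so the gatekeeping test does not hold 5%. Under the stated assumptions (k = 2 to 8, normal noise, independent sessions, joint 3-df test, n = 24, SD 0.12 ng/mL), the false rejection rate runs from barely above nominal at 2% noise to 94% at 25% noise. Which applies cannot be settled from the documents.

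A reader might infer that the trial's Aim 1 conclusion will be wrong. That does not follow. If the true rise is near 0.15 ng/mL, most of it remains after subtracting any bias in the 2–25% range, and the conclusion would probably survive. The defect is that a significant result is not by itself evidence of an effect, and this matters most if the response is attenuated at the later sessions. It should be corrected before analysis, because the test carries the gate and the correction is cheap.

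**What to change.** Define the primary ΔCTX as the plasma-volume-adjusted change from a stated baseline (one named pre-exercise sample, or the mean of the two) to one prespecified recovery time, or to the mean or time-averaged AUC of prespecified recovery times. Choose the times from the sponsor's earlier data. The documents do not establish when CTX peaks, so they give no ground for restricting the window to 120 min or any other limit.

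Test this change as a contrast in the repeated-measures model. The mixed model already planned as secondary covers all time points. Report peak ΔCTX descriptively only, use the same definition in protocol and SAP, and restate the expected effect, SD and power for it.

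The cost is wording and a revised power statement; no new samples are needed. The downside is that a fixed-time or averaged change may be smaller than the peak change. With 24 evaluable participants, about 90% power is kept down to d = 0.69, which at an SD of 0.12 is 0.69 × 0.12 ≈ 0.083 ng/mL, or 55% of the planned 0.15.
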